5.4 Staff questionnaires (see appendix for instrument)

5.4.1 Site PIs will submit to CHOP for recruitment

- Email addresses of potential health professional subjects

5.4.2 The questionnaires will include the following elements:

- Hospital
- Unit(s) where person worked during the intervention period
- Profession (nurse, attending physician, etc.)
- Did the person care for any patients with bronchiolitis on an intervention unit during the intervention period?
- Gender, race, ethnicity of subject completing the questionnaire
- Acceptability of Intervention Measure (AIM)
- Intervention Appropriateness Measure (IAM)
- Feasibility of Intervention Measure (FIM)

- Supplemental items (see appendix)

Please note that we may make minor changes to the items included in the questionnaire in the months between initial IRB submission and questionnaire administration based on ongoing discussion with the investigative team and site PIs. As long as the changes do not represent major changes in scope, we will not submit revised versions of the questionnaire to the IRB.

6 STATISTICAL CONSIDERATIONS

This is a feasibility study preparatory to a clinical trial. Therefore, there is minimal emphasis on statistical power.

6.1 Primary Endpoint

The primary endpoints are the resulting scores on the questionnaire measures above.

6.2 Secondary Endpoints

Secondary endpoints will include the following:

- Continuous pulse oximetry use rates in children with bronchiolitis who are not requiring supplemental oxygen administration.
- The test characteristics (sensitivity, specificity, positive predictive value, negative predictive value) of the electronic health record data from the medical monitoring device for actual monitoring at the bedside in bronchiolitis

6.3 Statistical Methods

6.3.1 Questionnaire-based methods (AIM, IAM, FIM)

We will generate average scores for each item and for each measure, stratified by hospital and role (e.g. nurse, physician).

6.3.2 Pulse oximetry use rates

We will calculate the overall rate of SpO₂ monitoring overuse within each hospital. The rate numerator is the number of patients with bronchiolitis who are breathing room air (not requiring any supplemental oxygen) and are continuously SpO₂-monitored. The rate denominator is the total number of patients with bronchiolitis who are breathing room air. We will stratify these rates by key variables (e.g. time of day, amount of time off supplemental oxygen).

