1 BACKGROUND INFORMATION AND RATIONALE

1.1 Introduction

Continuous pulse oximetry (SpO₂) monitoring has revolutionized detection of oxygen desaturation in operating rooms and other high-risk areas, improving outcomes in those settings.^{1,2} However, research suggests that overuse of continuous SpO₂ monitoring in stable children with bronchiolitis who are unlikely to benefit from it is low-value care that places some children at risk of adverse outcomes.³⁻¹²

Despite national guidelines^{13,14} discouraging continuous pulse oximetry use in stable bronchiolitis patients, 46% of those infants and children are continuously monitored (not yet published data from a multicenter study performed in 56 hospitals led by investigators on this proposal).

This study aims to pilot an audit and feedback strategy to align continuous pulse oximetry use in stable bronchiolitis patients with evidence and guideline recommendations in preparation for a multicenter cluster-randomized hybrid trial.

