In this study that included over 3600 in-person assessments of pulse oximetry monitoring status, we found that the overall monitoring rate across all hospitals was 46%, with a very wide range of variation, ranging from hospitals that monitor $<5\%$ of these patients to hospitals that monitor $>85\%$ of these patients (results not yet published; see figure below). These results support efforts to reduce continuous pulse oximetry in stable bronchiolitis patients in outlier hospitals with high use rates.

Prior to submitting a subsequent grant that will aim to de-implement continuous pulse oximetry in a well-defined stable bronchiolitis population, we must establish the feasibility of a foundational audit and feedback strategy for addressing continuous pulse oximetry overuse.

Continuous pulse oximetry overuse rates (by hospital, unadjusted, with 95% CIs)

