4.2 Intervention period

- Implementation teams will conduct data collection rounds and supplemental chart review (see Section 5) to determine continuous pulse oximetry status on bronchiolitis patients not receiving supplemental oxygen or room air flow, targeting data collection at least twice per week in order to acquire sufficient data for audit and feedback intervention.
- If any hospital staff responsible for the care of the patient are present and available on the unit, the data collector may perform real-time inquiry if feasible, briefly asking about the indications for monitoring individual patients, which will be documented in the study database as field notes without documenting any of the hospital staff member's identifiers.
- On a weekly basis, the data will be summarized in a dashboard and the dashboard along with the raw data will be returned to the site PI.
- Local implementation team will then share that data in electronic and in-person settings appropriate and tailored to each site (e.g. email, safety huddles,^{24,25} staff meetings, rounds, staff messages in electronic health record systems) with key clinician stakeholders who order or manage continuous pulse oximetry monitoring for bronchiolitis patients. Data will be contextualized with (a) the hospital's prior performance, (b) other hospitals' prior performance, (c) the current performance of other units in the same hospital, (d) the current performance of other units in other hospitals.
- Additional educational materials will be distributed and additional education/outreach sessions will be held by the local implementation team at a frequency determined by the site PI depending on local pulse oximetry use rates.

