5.2 Chart review

5.2.1 Site investigators will provide the following contextual information about audit and feedback and educational outreach delivery events, using a framework previously described:²⁹

- Date of event
- What type of session was held? (audit data review, educational outreach session, email, webinar, etc)
- Who was the audience (role composition, (e.g. nurses and residents from the 3 East unit)
- What information was delivered?
- Were specific behavior changes in response to the data discussed?
- Were structural changes discussed?
- Were other changes discussed?
- Were comparison data discussed?
 - The same hospital's past season performance
 - Other hospitals' past season performance
 - Other hospitals' current season performance
 - Performance of other units in the same hospital during current season
 - Performance of other units in other hospitals during current season
- Were graphs presented?
- How fresh were the most recent data discussed? (e.g. from the previous week)
- Implementation dates and details of any active quality improvement projects occurring concurrently

5.2.2 The following data elements will be abstracted from the chart and stored in the study database:

- Hospital
- Admission date and time
- Coded patient-admission ID – this is an identifier for each unique patient-admission to allow the data analysis to account for clustering of observations within individual patient-admissions. This is not an actual patient identifier assigned by the hospital; it is a study-specific coded identifier with the linkage master list document held by the individual site (no

actual patient identifiers other than the dates listed here are transmitted to CHOP from other sites).

- Unit name
- Bed number
- Patient age
- Patient sex
- Patient race and ethnicity
- Patient primary diagnosis and chronic conditions
- Forms of chronic neurologic impairment (e.g. static encephalopathy, cerebral palsy, hydrocephalus, spina bifida, epilepsy/seizure disorder, hypotonia, other form of neurologic impairment)
- Technology dependence (e.g. short-term feeding tube, long-term feeding tube, central venous line, renal dialysis)
- History of apnea or cyanosis during this illness
- History of ICU stay earlier in this admission
- Patient gestational age
- How long have they been off respiratory support (e.g. supplemental oxygen or room air flow), according to the chart?

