5.3 Bedside visual observation “rounds”

- Date and time rounds occurred at this patient’s bedside (the exact time, to the minute, using the time displayed on the bedside monitor as the time of record)
- Based on observing the patient at the bedside, are they currently receiving any respiratory support (e.g. supplemental oxygen or nasal cannula flow)?
- Are they being continuously pulse oximetry monitored right now based on bedside observation?
- Are they being continuously electrocardiographically/cardiorespiratory monitored (using chest leads to measure heart rate, heart rhythm, and/or respiratory rate) right now based on bedside observation?
- Field notes based on brief real time inquiry of health care professionals, if performed, regarding why the patient is continuously monitored

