8.3 Confidentiality

All data and records generated during this study will be kept confidential in accordance with Institutional policies and HIPAA on subject privacy. The Investigator and other site personnel will not use such data and records for any purpose other than conducting the study.

The only PHI elements that documented in the study database are the admission date and the date the data collection rounds occurred (which by definition is a date during the patient's hospitalization). Thus this is a *limited dataset*.

The dataset is also *coded* to decrease the risk of breach of confidentiality. A patient-admission ID number not otherwise associated with the individual (not derived from any element of PHI) will be generated by each site and included in the study database allowing patients to be followed over time within the same admission. This is an identifier for each unique patient-admission to allow the data analysis to account for clustering of observations within individual patient-admissions. This is not an actual patient identifier assigned by the hospital; it is a study-specific coded identifier with the linkage master list document held by the individual site (no PHI other than the dates listed above are transmitted to CHOP from other sites).

Hospitals that choose to maintain paper master lists will keep them in locked file cabinets. Hospitals that choose to maintain electronic master lists will store them either on hard drives owned by the institution or servers maintained/approved by their institution. The master list containing the key to decipher the coded dataset will be deleted/destroyed at the earliest possible date that complies with individual hospitals' retention of records policies.

Questionnaire data will not contain any PHI.

No identifiable data will be used for future study without first obtaining IRB approval. The investigator will obtain a data use agreement between provider (the PI) and any recipient researchers (including others at CHOP) before sharing a limited dataset (dates and zip codes).

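### Does counting patients in section 6.3.2 leave the pulse oximetry use rate without a workable unit for children seen on several rounds?

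*Combined protocol and SAP*

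**What the plan says.** Section 6.3.2 sets a rate within each hospital. The numerator is patients with bronchiolitis on room air who are continuously monitored. For the denominator it says: "The rate denominator is the total number of patients with bronchiolitis who are breathing room air". It continues: "We will stratify these rates by key variables (e.g. time of day, amount of time off supplemental oxygen". It names no confidence interval.

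The data behind the rate are bedside checks. Section 5.3 asks, at a time recorded to the minute: "Are they being continuously pulse oximetry monitored right now based on bedside observation". Section 4.2 targets rounds at least twice a week, with no maximum. Section 8.3 says the coded patient-admission ID is "included in the study database allowing patients to be followed over time within the same admission". Section 5.2.2 says the ID is there "to allow the data analysis to account for clustering of observations within individual patient-admissions". Section 6.3 does not mention the ID.

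For the earlier 56-hospital study, section 1.1 says "46% of those infants and children are continuously monitored", while section 1.2.5 reports "over 3600 in-person assessments of pulse oximetry monitoring status, we found that the overall monitoring rate across all hospitals was 46" percent. Section 4.2 puts current results beside earlier ones: "Data will be contextualized with (a) the hospital's prior performance".

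**The concern.** Read literally, a count of patients gives each child one entry. Time of day and time off oxygen belong to a round, so a child seen twice can fall in two strata, and can be monitored at one check and not at the other. Section 6.3.2 does not say what to do with that child. One entry per child would also leave no clustering within admissions, although the ID is collected for that purpose.

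Two things would be at stake. First, two analysts could report different rates from the same data. If a child counted as monitored when monitored at any round, a child taken off monitoring between rounds would stay in the numerator, which would hide the change the feedback is meant to encourage. A rate per child would also not compare directly with an earlier rate per assessment. Second, with no interval method named, someone could treat repeated checks on one child as independent and report an interval that is too narrow.

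**Working it through.** The documents state no sample size, power or precision for this rate, so there is no figure to reproduce. The check has two parts: which unit the text implies, and how much the choice could matter.

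**Which unit the text implies**

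- Section 6.3.2 is in the present tense (children who are on room air and are monitored), which describes a state at one moment.
- Sections 5.1 and 5.3 record current status at the bedside. Section 5.1 likens this to momentary assessment.
- The strata in section 6.3.2 have a single value only at a given round.
- Sections 5.2.2 and 8.3 speak of several observations per admission and intend the analysis to account for them.
- Sections 1.1 and 1.2.5 give the same 46%, once as a share of children and once over assessments. The authors therefore already write of children being monitored when they count assessments.

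All five fit one reading: sum the eligible children present at each round. Under it the strata add up to the total, the units match the earlier study, and the ID has a use. Rules based on any, every, first or last round appear nowhere.

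**How much the choice could matter**

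Inputs from the documents: participation of at least 1 day, 1 to 3 days on average (3.3.1); two rounds a week as the minimum (4.2), taken as one every d = 3.5 days; at most 300 children per hospital (3.3.2); rate p = 0.46 (1.2.5). Assumed: stay L = 1 day plus an exponential time with mean b, so the average stay is 1 + b; within-child correlation (ICC) 0.4 to 0.8.

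*Share of observed children seen again* = E[min((L − d)⁺, d)] / E[min(L, d)]
= b·e^(−2.5/b)·(1 − e^(−3.5/b)) / [1 + b(1 − e^(−2.5/b))]

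- Average 1 day: every stay is 1 day, so 0%.
- Average 2 days (b = 1): 0.0796 / 1.918 = 4%.
- Average 3 days (b = 2): 0.473 / 2.427 = 20%.

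A purely exponential stay, which ignores the 1-day minimum, gives e^(−3.5/m) for an average of m days: 3%, 17% and 31% for m = 1, 2 and 3.

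*Rates under other counting rules, 3-day average.* For a child with two checks:

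- Any = 1 − (0.54² + ICC × 0.2484) = 0.609 at ICC 0.4 and 0.510 at ICC 0.8.
- Every = 0.46² + ICC × 0.2484 = 0.311 and 0.410.

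The proportions of observed children with one, two, and three or more checks are 0.805, 0.161 and 0.034. Averaging beta-binomial probabilities over these gives 49% and 47% for any, and 43% and 45% for every. The rate per observation stays at 46%.

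*Interval, 3-day average.* Mean checks per observed child = 3 / 2.427 = 1.236, so 300 children give about 371 observations. The design effect is 1 + ICC × E[n(n − 1)]/E[n], where n is the number of checks on an observed child. The second factor is 2 × 0.195/(1 − e^(−1.75))² / 1.236 = 0.462, so:

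- Design effect: 1.185 at ICC 0.4 and 1.370 at ICC 0.8; square roots 1.089 and 1.170.
- Half-width ignoring clustering: 1.96 × √(0.2484/371) = 5.1 points.
- Half-width with clustering: 5.5 and 5.9 points, that is 9% and 17% wider.

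**The case for a change.** The strongest case for a change is that section 6.3.2 is incomplete on either reading. If children are counted once, it lacks a rule; if observations are counted, it lacks a method for the clustering that sections 5.2.2 and 8.3 announce. Section 3.3.2 counts unique patients, so the literal reading is open. Two or three sentences and no new data would settle it. The earlier study's figure carried 95% intervals by hospital, and this rate has none planned.

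The schedule is also only a minimum. With daily rounds and a purely exponential 3-day average stay, 72% of observed children are seen again, and the any and every rules give 52% to 64% and 28% to 40%. Ignoring clustering would then matter: the design-effect factor is 2 × 0.717/0.283 = 5.06, so the interval should be √(1 + 0.4 × 5.06) = 1.74 to √(1 + 0.8 × 5.06) = 2.25 times as wide.

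This stands in part. The unit is not written out, the interval is absent, and the effects grow when rounds are frequent or close together. But the divergent rates need a rule that no section proposes, and the too-narrow interval needs an analyst to set aside the stated purpose of the ID. On the reading that the other sections support, the rate is the same kind of quantity whatever the schedule.

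**Conclusion.** No change to the plan follows. Section 6.3.2 leaves a detail unstated that an analyst can fill from the rest of the document: the unit is the eligible bedside observation, and any interval should be clustered on the patient-admission ID. Followed that way, the plan gives a sound descriptive rate for each hospital, comparable with the earlier study. The missing interval is an omission in a single-arm feasibility pilot whose section 6 places little weight on power; no test and no stated precision depends on this rate.

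At the minimum schedule the stakes are small: 0% to 20% of observed children seen again, counting rules within about 3 points of 46%, and an interval 9% to 17% wider at the 3-day average. These figures rest on evenly spaced rounds, the 1-day minimum plus an exponential tail, and an assumed correlation of 0.4 to 0.8, which the documents do not give. With daily rounds the unit and the clustering would matter much more, but the sensible reading would be the same.

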6.3.3 Medical device integration test characteristics

We will calculate the sensitivity, specificity, positive predictive value, negative predictive value of the electronic health record data from the medical monitoring device for actual monitoring at the bedside in bronchiolitis.

6.4 Sample Size and Power

By engaging 10 sites in a range of different settings, we expect to gain meaningful insight into the feasibility of performing a larger trial of this intervention. By collecting a total of approximately 100 questionnaires on each of the AIM, FIM, and IAM per hospital, we will have 90% power to reject the null hypothesis response of “Neither agree nor disagree” (3.0) assuming a mean response of “Agree” (4.0), alpha=.05, standard deviation=3. A total of 73 responses would provide 80% power to detect the above conditions.

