3.3.2 Total Number of Study Sites/Total Number of Subjects Projected

The study will be conducted in up to 10 hospitals in the United States.

Primary subjects exposed to the intervention (hospital staff): Since the intervention is occurring at a unit-wide level and we are not collecting any identifiers on these primary subjects, it is not possible to accurately measure the actual number of staff whose behavior could potentially have been impacted by the intervention. It also will not be possible to identify when hospital staff are exposed to the intervention repeatedly over time. In order to best estimate this number, we will "count" the

involvement of 100 hospital staff per unit during the entire intervention period. Based on an average of 5 available units per hospital in candidate hospitals, we can estimate 10 hospitals * 5 units per hospital * 100 staff per unit = 5,000 hospital staff subjects, acknowledging that this number will not be completely accurate but is a reasonable estimate. When we report the “actual” number of primary exposed subjects involved for continuing reviews and study closure, we will report 100 * the total number of units involved in the study.

Primary subjects completing the questionnaires (hospital staff): We will aim for 100 completed questionnaires per hospital x 10 hospitals = 1,000 primary subjects completing the questionnaires. Since these 1,000 will be drawn from within the 5,000 listed above, they will not add to the overall subject total.

Secondary subjects - Patients: We project collecting data on a maximum of 300 unique bronchiolitis patients per hospital * 10 hospitals = 3,000 patients.

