10.2 Draft questionnaire items

See eIRB application section 12.02 2.0.

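### Section 6.4 bases its power on SD=3, more than the implied 1–5 response scale allows; with independent responses the stated power is too low, a conservative and minor error

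*Combined protocol and SAP*

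**What the plan says.** Section 6.1 makes the questionnaire scores the primary endpoints: "The primary endpoints are the resulting scores on the questionnaire measures above". Section 6.4 gives the only power statement for them. The test is against "the null hypothesis response of “Neither agree nor disagree” (3.0) assuming a mean response of “Agree” (4.0"). Power is put at 90% for about 100 questionnaires per hospital on each of the three measures, and the statement closes with "alpha=.05, standard deviation=3. A total of 73 responses would provide 80% power to detect the above conditions". Section 3.3.2 sets the matching target: "We will aim for 100 completed questionnaires per hospital x 10 hospitals = 1,000 primary subjects completing the questionnaires".

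Section 6.3.1 analyses averages, by item and by measure, within hospital and role. The SD in section 6.4 therefore belongs to the response scale itself. No source is given for the value 3.

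The documents do not print the score range. For the questionnaire items, section 10.2 says only "See eIRB application section 12.02 2.0". Section 6 opens with a general caveat: "This is a feasibility study preparatory to a clinical trial. Therefore, there is minimal emphasis on statistical power".

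**The concern.** On a bounded scale the mean limits the SD. With neutral at 3.0 and Agree one point higher at 4.0, the natural symmetric scale runs from 1 to 5. An SD of 3 on such a scale would exceed half its range, which no set of responses can produce.

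The printed 73 and the 90% and 80% figures all follow from that SD, so they do not describe the test the plan sets out. The practical stake is small. A reader would take 73 as the number needed for 80% power, and a site with fewer returns could wrongly be judged to fall short.

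**Working it through.** **Inputs.** From section 6.4: null mean 3.0, assumed mean 4.0 (difference 1.0), alpha .05, SD 3, n=100 and n=73. The number of sides is not stated. From section 6.3.1: scores are averages. Inferred from the anchors: range 1–5.

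**1. Reproducing the plan's figures.** For a one-sample t-test, power comes from the noncentral t distribution with n−1 degrees of freedom and noncentrality (difference/SD)·√n.

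- n=100: noncentrality (1/3)·10 = 3.33; two-sided power 91.0%.
- n=73: noncentrality (1/3)·8.54 = 2.85; two-sided power 80.2%.
- Smallest n: 73 for 80% and 97 for 90%.

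A one-sided test would need 58 and 79, so the two-sided test is the one that was used. SD=3 is the input that produced the printed 73, not a misprint beside a correct result.

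**2. Largest possible SD.** On a scale from a to b with mean m, the SD is at most √((b−m)(m−a)).

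- 1–5, mean 4.0: √((5−4)(4−1)) = √3 = 1.73.
- 1–5, any mean: largest at m=3, √((5−3)(3−1)) = 2.0.
- With the n−1 denominator, the sample maximum at mean 4.0 is 1.73·√(100/99) = 1.74 for n=100.

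**3. Could another range rescue SD=3?**

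- 0–6 also centres on 3.0, but allows only √((6−4)(4−0)) = 2.83 at mean 4.0.
- 1–7 allows √((7−4)(4−1)) = 3.0 at mean 4.0, but its midpoint is 4.0, which contradicts a neutral value of 3.0.
- A sum over several items could have SD 3, but 3.0 and 4.0 are single-response values and section 6.3.1 uses averages.

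**4. Power at SDs the scale allows (two-sided t-test, independent responses).**

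| SD | Power, n=73 | Power, n=100 | n for 80% | n for 90% |
|---|---|---|---|---|
| 3 (as stated) | 80.2% | 91.0% | 73 | 97 |
| 2.83 (maximum at mean 4.0 if 0–6) | 84.6% | 93.8% | 65 | 87 |
| 2.0 (maximum on 1–5 at any mean) | 98.8% | 99.9% | 34 | 44 |
| 1.73 (maximum on 1–5 at mean 4.0) | 99.8% | 99.99% | 26 | 34 |

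**5. Check on the t-test formula.** The only 1–5 distribution with mean 4.0 and SD 1.73 is 25% ones and 75% fives. Summing the exact binomial probabilities for it gives t-test power of about 82% at n=26, 88% at n=34, 99.6% at n=73 and 99.97% at n=100. The 34 is therefore approximate for 90% in that extreme case. The statement that power exceeds 99% at 73 and 100 holds exactly.

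**6. Clustering by unit.** SD 1.73 acts like SD 3 at a design effect of (3/1.73)² = 3.0. Section 3.3.2 takes 5 units per hospital, so 100 questionnaires would be 20 per unit if spread evenly (an assumption). Then 1 + 19·ICC = 3.0 gives ICC = 0.105. The documents give no ICC. For SD 1.73 and n=100, replacing the SD by 1.73·√(design effect):

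| Assumed ICC | Design effect | Power, 99 df | Power, 4 df (5 units) |
|---|---|---|---|
| 0.05 | 1.95 | 98% | 86% |
| 0.10 | 2.90 | 92% | 72% |
| 0.15 | 3.85 | 83% | 60% |
| 0.20 | 4.80 | 74% | 52% |

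These are worst cases for the SD. At an assumed SD of 1.0 and ICC 0.10, the 4-df power is about 99%.

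**The case against.** The strongest reply is that nothing depends on this SD. It is an openly stated assumption that errs on the safe side. The plan gives power little weight, section 6.3.1 plans averages with no hypothesis test, and the target stays the same whichever SD is used. All of that stands, and it keeps the point minor. It does not make the printed figures right.

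A second reply is that the 1–5 range is inferred, because the items sit in the eIRB application. That also stands, so the finding is conditional on the range. The inference is nevertheless strong: among the ranges checked, none centred on 3.0 allows an SD of 3 at mean 4.0.

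A third reply is that SD=3 might be a deliberate margin for staff grouped in units. Section 6.4 does not say so. It calls the 3 a standard deviation and states no design effect.

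Three stronger readings are tempting, and the documents support none of them:

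- *The study is mis-sized or underpowered.* The SD error runs the other way. With independent responses the stated powers are lower bounds.
- *SD=3 will be carried into the later trial.* Sections 1.1 and 1.2.5 describe that trial as aimed at de-implementing continuous oximetry. Nothing says it will be sized on these questionnaire means, and up to 1,000 pilot questionnaires would supply an observed SD.
- *100 per hospital is sufficient even with clustering.* That depends on an ICC, a spread of responses over units and an analysis that the plan does not give. The second table shows how widely the answer moves.

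**Conclusion.** The point holds as a minor correction to an input, not to the arithmetic. If the scores run from 1 to 5, an SD of 3 is impossible. The stated 90% and 80% then understate power for independent responses: at the largest SD possible at mean 4.0, power is above 99% at both 73 and 100. The printed 73 is 73/26 = 2.8 times the number that the t-test formula needs for 80%.

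The conclusion rests on the inferred 1–5 range, averaged scores, a two-sided one-sample t-test and independent responses. Without independence the size of the understatement is unknown, and no assurance about 100 per hospital follows in either direction. No target, site number, data collection or analysis changes.

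**What to change.** In section 6.4:

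- State the score range of the three measures, or cite the eIRB section that gives it.
- Replace SD=3 with a sourced SD that the range allows. If none is available, use the scale maximum.
- Restate the power at n=100 and n=73 as conditional on independent responses, and say that the test is two-sided and whether the 73 is per hospital.

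If the scale maximum is used, suitable wording would be: *On a 1–5 score the SD at mean 4.0 cannot exceed 1.73. If responses are independent, 73 or 100 questionnaires each give more than 99% power (two-sided one-sample t-test, alpha .05) to reject 3.0 when the mean is 4.0. This makes no allowance for clustering of staff within units.*

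If SD=3 was meant to cover clustering, say so as an explicit design effect and show power over a range of assumed ICCs, as in the second table.

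The cost is one or two sentences in section 6.4, plus a short table if clustering is addressed. The questionnaire target and all procedures stay as they are.
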